7.2.5. Blood Pressure/Pulse (Sitting and Standing)

Blood pressure (mm Hg) should be measured using a manual aneroid or mercury sphygmomanometer with a cuff appropriate to the subject's arm girth placed over the bare skin. Subjects should rest sitting with feet flat on the floor at least 5 minutes before sitting blood pressure readings are taken. The sitting pulse rate (beats/minute) should be measured after the blood pressure. Pulse rate should be measured for at least 30 seconds.

After standing for approximately 2 minutes, another blood pressure reading will be taken followed by a standing pulse reading.

Whenever possible, the subject should refrain from products containing nicotine or caffeine 2 hours before taking blood pressure measurements. Also, whenever possible, blood pressure measurements should be taken on the same arm throughout the study.

Blood pressure and pulse will be measured according to the [Schedule of Activities](#). At Visit 6/Week 4, subjects will take their morning study medication during the visit. Blood pressure and pulse will be measured before study medication dosing (trough).

7.2.6. 12-lead Electrocardiogram (ECG)

A 12-lead ECG will be conducted at various time points according to the [Schedule of Activities](#).

Readings and interpretations of ECG tracings will be performed centrally. Information to be reported by the central scoring site will include the subject's demographic information; beats per minute (bpm); overall interpretation; rhythm type; respiratory rate; heart rate intervals PR, QRS, QT, QTcF (ms), and QTcB (ms); and any comments. The values of QTcF will be used for clinical decision making and interpretative assessment of changes in QTc. QTcB will be measured to enable comparisons with historical data but not used for clinical decisions due to inaccuracies of the Bazett's formula in correcting for heart rate.

All ECGs must be obtained before or at least 3 hours after food intake. ECGs must be obtained **prior to blood pressure/pulse measurements and prior to collection of any blood sample** CCI because these assessments can affect the ECG. To standardize the collection procedure, the ECG should be collected in a comfortable and quiet place after the subject has been allowed to rest in a supine position for approximately 5 minutes.

Baseline and Visit 6 (end of treatment/early termination) ECGs must be administered in triplicate, tracings should be collected approximately 2 minutes apart.

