At the Day 29/Week 4 visit, subjects will take their morning medication with food at the visit. An ECG will be done before dosing.

All ECGs must be reviewed for safety (including a review of the QTcF value) at the site by a physician within a reasonable time from the day of the recording [48 hours is recommended], signed and dated by the reviewing physician and retained in the subject's study records.

Participation in the study is contingent on the subject having both screening and baseline ECGs without clinically significant abnormalities.

ECGs showing a QTcF of ≥ 480 msec or a suspected increase of QTcF from baseline of 60 msec or greater must be repeated within the same visit. If the QTcF value persists at ≥ 480 msec and/or the change from baseline persists at ≥ 60 msec, the study drug must be discontinued immediately and a pediatric cardiologist or an adult cardiologist experienced in the interpretation of pediatric ECGs should be contacted to discuss the ECG result (see [Section 6.7.1](#)).

If discontinued, the subject will not be eligible to enter the open-label extension trial.

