7.2.7. Child Depression Rating Scale – Revised (CDRS-R)

The Child Depression Rating Scale – Revised¹⁷ (CDRS-R) is a clinician-rated scale that assesses 17 distinct symptom areas to derive an index of depression severity. Though originally developed for children 6-12 yrs, it has been widely used with adolescents and its developers recommend it for both children and adolescents.¹⁸ Clinicians' ratings are based on information obtained from interviews with both child and parent (or guardian) informants;

interview guides have been developed to structure the interview to ensure all 17 symptom areas are assessed. For this trial, the manual's recommendations on resolving discrepancies between informants will be used (ie, most impaired rating given by valid informant will be assigned). It takes about 20-30 min to administer and rate the CDRS-R. Ratings are assigned on a 7-point scale (ranging from 1-7, with higher values indicating greater impairment). A total scale score is calculated by summing the 17 items. The total score on the CDRS-R will be used to assess changes in depression severity over time between treatment groups.

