7.6. Triggered Requirements

The following specific cardiac safety parameters of concern for the compound require the following action to be taken (see also [Section 6.7.1](#)):

Condition	Action
QT Prolongation	ECGs are to be reviewed and compared to baseline to assess potential changes. ECGs showing a QTcF of ≥ 480 msec or a suspected increase from baseline of 60 msec or greater must be repeated within the same visit. If the QTcF value persists at ≥ 480 msec and/or the change from baseline persists at ≥ 60 msec, the study drug must be discontinued immediately and a pediatric cardiologist or an adult cardiologist experienced in the interpretation of pediatric ECGs should be contacted to discuss the ECG result. Verified increase in QTcF of ≥ 60 msec or verified occurrence of QTcF ≥ 480 msec will be considered as an adverse event of QTc prolongation. QTcB prolongation (Bazett's correction) will not be used to define adverse events; QTcB will be measured only to enable historical comparisons.
Ventricular Arrhythmia	An ECG showing ventricular arrhythmia (except occasional ventricular extrasystoles) should be followed up with a rhythm strip ECG and Pfizer must be notified. In addition, a stat over read from the central vendor should be requested, a pediatric cardiologist or adult cardiologist experienced in the diagnosis and treatment of pediatric arrhythmias should be consulted, and the subject monitored, as necessary. If the ventricular arrhythmia is confirmed, the subject must be discontinued from the study.

Condition	Action
Syncope	All syncopal episodes suggestive of cardiac arrhythmia (sudden loss of consciousness, loss of postural tone, and no pre-syncopal phase), except vasovagal syncope will be considered adverse events and the subject will be discontinued from the study. Every effort should be made to obtain vital signs and an electrocardiogram at the time of the event. Further evaluation, eg, Holter monitoring, may also be useful. Subjects experiencing syncope of probable vasovagal origin (onset not sudden but preceded by a pre-syncopal phase, presence of predisposing factors such as blood sampling procedure, standing, hot shower, hair curling, etc) will also be considered adverse events but subjects may continue study participation after sponsor approval.

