6. ENDPOINTS AND COVARIATES

For summaries and analyses of change from baseline, baseline is defined as the pre-dose measurements for variables that have assessment at the Baseline Visit (Day 1), and it is defined as the most recent assessment prior to randomization for variables that have no assessment at the Baseline Visit. For the electrocardiogram (ECG) data, baseline will be defined as the mean of the pre-dose triplicates at the Baseline Visit.

For collection schedules for all endpoints, please refer to the protocol.

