8.2.5. Safety Analyses

The safety assessments include:

- *Adverse Event Reporting;*
- *Concomitant treatment*
- *Clinical Laboratory Testing;*
- *Physical Examinations;*
- *Blood Pressure and Pulse;*
- *Height and Weight, BMI, BMI z-score, and waist circumference;*
- *Electrocardiogram.*

A 3-tier analysis approach described below will be used to analyze adverse events. No formal statistical analysis will be conducted on any of the other safety data listed above.

Data for height, weight, BMI, and waist circumference will be summarized by timepoint using descriptive statistics. Additionally, height, weight, and BMI will be standardized using CDC growth charts and the resulting z-scores presented in listings and frequency tables in 1-unit intervals. In addition, frequency tables of above/below a 1-point increase in the z-scores for BMI will be presented.

All randomized subjects who receive at least one dose of study drug will be included in the safety analysis. All adverse events that are observed from the time of first dosing with study medication (at randomization) until the end of study participation will be included in the safety analysis. Adverse events that occurred during treatment with the antipsychotic medication will be reported separately if the event occurred prior to randomization.

All adverse events will be coded according to the Medical Dictionary for Regulatory Activities (MedDRA) and will be summarized by treatment group. The incidence of treatment-emergent adverse events will be tabulated by treatment group and by system organ class. In addition, the incidence of serious adverse events and adverse events that cause withdrawal will be tabulated. All adverse events will be listed.

The following 3-tier approach will be used to summarize AEs. Under this approach, AEs are classified into 1 of 3 tiers. Different analyses will be performed for different tiers and will be documented in the statistical analysis plan as follows:

Tier-1 events: These are pre-specified events of clinical importance and are maintained in a list in the product's Safety Review Plan. This list may be updated, as more is understood about the drug.

Tier-2 events: These are events that are not tier-1 but are "common". A MedDRA Preferred Term (PT) is defined as a tier-2 event if there are at least 4 in any treatment group.

Tier-3 events: These are events that are neither tier-1 nor tier-2 events.

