Centrally over-read ECG variables will be summarized by mean change from baseline to each measurement time for heart rate, PR interval, QRS width, QT interval and QTcF (Fridericia correction) values. Baseline will be defined as the mean of the pre-dose triplicates at the Baseline Visit. Additionally, the incidence of categorical increases in QTc intervals will be provided. Categories for QTcF are ≥ 450 msec, ≥ 480 msec, and ≥ 500 msec. Categories for QTcF as change from baseline are ≥ 30 msec increase and ≥ 60 msec increase. QTcF is considered the primary QTc value for measurements of change and for clinical decision making as this correction is more accurate with changes in heart rate. To enable historical comparisons, categorical changes in QTcB (Bazett’s correction) also will be tabulated but clinical decisions and interpretation of data will be based on QTcF values.

The frequency of prior and concomitant medications will be summarized by treatment based on the WHO-drug coding dictionary.

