8.2.6. Analyses of Special Safety Endpoints

The special safety assessments include:

- *CDRS-R;*
- *C-SSRS;*
- *Movement Disorder Scales (SARS, BAS, and AIMS).*

For special safety assessments, descriptive statistics (n, mean, standard deviation, min, max, 95% CI) by treatment group and visit for the change from baseline will be provided.

For CDRS-R, a listing by treatment group and visit will be generated to include all the CDRS-R ratings for any subject who at any visit had a CDRS-R total score of 40 or more. These are subjects with the potential of developing depression.

For all of the Movement Disorder Scales, descriptive statistics by treatment group and visit for change from baseline will be provided. For the SARS, the total score from the sum of all 10 sub-items will be summarized. For the BAS, only the global clinical assessment item will be summarized. For the AIMS, only the sum of the first seven items (ie, movement cluster) will be summarized. In addition, the same change from baseline MMRM model used for the primary and secondary endpoints will be applied to the Movement Disorder Scales.

The prospectively collected C-SSRS item responses will be mapped to the C-CASA suicidality event codes. No formal statistical hypothesis testing will be undertaken. Listings of both the C-CASA categories as well as the underlying C-SSRS scale data will be prepared. In addition, a summary table of C-CASA category frequencies at screening, baseline, and all post-baseline visits without regard to baseline will be compiled. Additional tables displaying post-baseline worsening and new-onset of suicidality within reporting categories (suicidal ideation) will also be prepared.

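### QTcF gets no ziprasidone-minus-placebo difference or confidence interval in the visible plan, and its tables do not say that Week 4 is a trough reading: a cheap improvement

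*SAP*

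**What the plan says.** **The risk.** Protocol 7.6 introduces its table thus: "The following specific cardiac safety parameters of concern for the compound require the following action to be taken". QT prolongation is the first row. SAP 8.2.5 makes QTcF the primary QTc measure.

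**The analysis.** SAP 8.2.5 states: "Centrally over-read ECG variables will be summarized by mean change from baseline to each measurement time for heart rate, PR interval, QRS width", continuing to QT and QTcF. It adds the incidence of QTcF at or above 450, 480 and 500 msec and of increases of at least 30 and 60 msec. Electrocardiogram is in the list to which this applies: "No formal statistical analysis will be conducted on any of the other safety data listed above". Protocol 9.8 matches. On baseline, SAP Section 6 says: "For the electrocardiogram (ECG) data, baseline will be defined as the mean of the pre-dose triplicates at the Baseline Visit".

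**The contrast.** For SARS, BAS and AIMS, SAP 8.2.6 says that "the same change from baseline MMRM model used for the primary and secondary endpoints will be applied to the Movement Disorder Scales".

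**ECG timing.** Protocol 7.2.6 on Week 4: "At the Day 29/Week 4 visit, subjects will take their morning medication with food at the visit. An ECG will be done before dosing". Its general rule is: "All ECGs must be obtained before or at least 3 hours after food intake". Protocol 5.3.3 has the drug taken with food, with doses about 12 hours apart. Protocol 7.2.5 calls the Week 4 pre-dose point the trough for blood pressure and pulse.

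**CDRS-R.** Protocol 7.2.7: "The total score on the CDRS-R will be used to assess changes in depression severity over time between treatment groups". SAP 8.2.6 gives descriptive statistics by arm and visit, and a listing of subjects who ever score 40 or more.

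**The concern.** Safety and tolerability is a primary objective, and this is a randomised placebo-controlled trial. For a continuous measure such as QTcF, the natural result is the difference between arms with its uncertainty. As planned, a reader would have to subtract two arm means and would have no interval for the result. The team already models other continuous safety measures between arms, so leaving out the compound's first-listed cardiac concern looks like an oversight and not a principle.

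Timing adds to this. An unlabelled Week 4 mean could be taken to describe the whole dosing interval when it describes the end of it. The Weeks 1 to 3 means may combine pre-dose and later post-dose readings, and titration is also under way in the first two weeks. Each by-visit figure therefore needs a label saying what it measures.

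**Working it through.** **1. Is a between-arm QTcF estimate planned anywhere visible?** Three places could hold one.

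- SAP 8.2.5, ECG paragraph: mean changes and category counts only, with no difference or interval.
- SAP 8.2.6: the MMRM covers SARS, BAS and AIMS; ECG is not among the special safety assessments.
- SAP 8.2.5, adverse-event tiers: tier-1 and tier-2 events get a risk difference with a 95% interval. Protocol 6.7.1 and 7.6 make a verified QTcF of 480 msec or more, or a rise of 60 msec or more, an adverse event, so this route exists.

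**2. How far does the adverse-event route reach?** The tier-1 list is in the Safety Review Plan, which is not among the documents. If QTc prolongation is not on it, tier-2 needs at least 4 cases in an arm. With 78 per arm, P(X ≥ 4) for X ~ Binomial(78, p), where p is an assumed true rate:

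| p | P(at least 4 cases) |
|---|---|
| 1% | 0.8% |
| 2% | 7% |
| 3% | 21% |
| 5% | 55% |

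Even no cases in 78 leaves a one-sided 95% upper limit of 1 − 0.05^(1/78) = 3.8%. A count of extremes also does not estimate a mean shift.

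**3. How many subjects supply Week 4 QTcF?** The plan sizes only YMRS, so I reproduce that first.

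- Total N = 4 × [8.0 × (1.960 + 1.036) / 4.55]² = 111.0. SAP 2.2 states 111.
- 111 / 0.62 = 179.03, rounded up to 180, as stated.
- 111 / 0.80 = 138.75. SAP 2.2.1 states approximately 138.
- 138 + 18 = 156, or 78 per arm. At 20% dropout, 78 × 0.80 = 62.4, so about 62 per arm at Week 4.
- The protocol's figures give nearly the same: 97 × 0.62 = 60.1.

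**4. What precision would the contrast have?** Half-width = t(0.975, 2n − 2) × SD × √(2/n). With n = 62, t = 1.98 and √(2/62) = 0.1796. The SD of QTcF change is an assumption.

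| Assumed SD (msec) | Standard error | 95% half-width (msec) |
|---|---|---|
| 10 | 1.80 | 3.6 |
| 12 | 2.16 | 4.3 |
| 15 | 2.69 | 5.3 |
| 18 | 3.23 | 6.4 |
| 20 | 3.59 | 7.1 |

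With all 78 per arm the range is 3.2 to 6.3 msec. This is a two-sample approximation to the MMRM contrast.

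**5. What does each visit measure?** The scheduled Week 4 ECG precedes the morning dose, about 12 hours after the evening one, so it is a trough value. At Weeks 1 to 3, drug taken with food plus the food rule means an ECG is either pre-dose or about 3 hours or more after a dose. No time since dose is set. Early-termination ECGs follow Visit 6 procedures with no fixed time since last dose, and the re-slotting rule in SAP Appendix 2 covers only YMRS, CGI-S and CGI-I.

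**The case against.** The best defence is that descriptive ECG summaries with outlier categories are a legitimate choice, and that protocol 9.8 and SAP 8.2.5 agree. That stands: there is no internal contradiction.

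Several stronger readings also fail.

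- A reader might infer that SAP 8.2.5 forbids any comparison of the arms. It excludes formal analysis; side-by-side means and category incidences remain open.
- A reader might infer that uneven timing at Weeks 1 to 3 biases the comparison. Both randomised, blinded arms follow one rule, so a difference there is a valid average over mixed times. The rule may even admit readings near the peak.
- A reader might want to scale the trough effect up to a peak effect. The documents give no time of peak or half-life, only that levels self-taper over 2 to 3 days, so no ratio can be supported.
- Text is redacted beside the Week 4 ECG timing in protocol 6.4 and within and after the safety analysis sections, and the SAP change log mentions M9 and M10 concentrations. A concentration-related analysis may exist, and its absence is not claimed.
- On CDRS-R, protocol 7.2.7 promises no model, and protocol 9.9 agrees with SAP 8.2.6. The by-arm intervals planned there are not, however, an interval for the difference.

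The adverse-event route answers the concern only in part, for the reasons in step 2 of the working.

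**Conclusion.** The point holds as a cheap improvement. The visible plan gives no placebo-corrected QTcF estimate or interval, and the ECG schedule supports a trough effect at Week 4 and a mixed-time effect at Weeks 1 to 3.

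It does not follow, as a reader might infer, that the trial cannot state the drug's QT effect. Randomisation, central reading and triplicates at baseline and Week 4 allow a trough difference to be estimated from ECGs the protocol already schedules, to within roughly 4 to 7 msec. What the schedule does not target is the effect at peak concentration.

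The precision rests on 20% dropout from 156 subjects and on an assumed SD of 10 to 20 msec. The finding that no contrast is planned rests on neither.

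**What to change.** Before unblinding:

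- **QTcF (SAP 8.2.5).** Fit the Section 8.1.1 change-from-baseline MMRM to QTcF at Weeks 1 to 4 in the Safety Analysis Set. Report the ziprasidone-minus-placebo difference with 95% confidence interval at each visit, as an estimate without p-values. Exempt it from the sentence excluding formal analysis.
- **Early-termination ECGs.** State how they are assigned to visits, and keep them out of any row labelled trough unless they are known to be pre-dose.
- **Labels.** Mark scheduled Week 4 ECG results as pre-dose (trough).
- **Time since last dose.** Report it where dose and ECG times were already recorded. Protocol 6.4 treats the clock time of the Day 28 evening dose as critical, so Week 4 may be recoverable. A new form field is not proposed: SAP version 1.2 follows the evaluability meeting, and a field added now could not time ECGs already taken.
- **CDRS-R (SAP 8.2.6).** Extend the movement-scale MMRM to the total score in the ITT set that SAP Section 5 assigns, with the same form of report.

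The cost is two extra model runs and table labels, with no extra ECG. The downside is a set of intervals unadjusted for multiplicity, which should be footnoted as descriptive.

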8.2.6. Analyses of Special Safety Endpoints

The special safety assessments include:

- *CDRS-R;*
- *C-SSRS;*
- *Movement Disorder Scales (SARS, BAS, and AIMS).*

For special safety assessments, descriptive statistics (n, mean, standard deviation, min, max, 95% CI) by treatment group and visit for the change from baseline will be provided.

For CDRS-R, a listing by treatment group and visit will be generated to include all the CDRS-R ratings for any subject who at any visit had a CDRS-R total score of 40 or more. These are subjects with the potential of developing depression.

For all of the Movement Disorder Scales, descriptive statistics by treatment group and visit for change from baseline will be provided. For the SARS, the total score from the sum of all 10 sub-items will be summarized. For the BAS, only the global clinical assessment item will be summarized. For the AIMS, only the sum of the first seven items (ie, movement cluster) will be summarized. In addition, the same change from baseline MMRM model used for the primary and secondary endpoints will be applied to the Movement Disorder Scales.

The prospectively collected C-SSRS item responses will be mapped to the C-CASA suicidality event codes. No formal statistical hypothesis testing will be undertaken. Listings of both the C-CASA categories as well as the underlying C-SSRS scale data will be prepared. In addition, a summary table of C-CASA category frequencies at screening, baseline, and all post-baseline visits without regard to baseline will be compiled. Additional tables displaying post-baseline worsening and new-onset of suicidality within reporting categories (suicidal ideation) will also be prepared.

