1.2.2.1.3. Study A1281134 (and Open Label Extension A1281135): Pediatric Schizophrenia

Pfizer conducted 2 Phase 3 studies to evaluate the effects of ziprasidone (oral capsules) in adolescents (age 13-17 years) diagnosed with schizophrenia. The A1281134 study was a 6 week, placebo-controlled double-blind trial to evaluate the efficacy and safety of flexible dose ziprasidone. Eligible subjects could continue in the open-label study A1281135, to evaluate the safety and tolerability of flexible dose ziprasidone over 26 weeks. The weight-based flexible titration regimens and target doses in these two studies were the same as in the pediatric bipolar studies A1281132 and A1281133. A planned interim analysis resulted in a recommendation from the Data Safety and Monitoring Board (DSMB) to terminate the A1281134 study due to futility. Pfizer terminated both studies; as a result participation of 1 subject in the A1281134 study and 92 subjects in the A1281135 study was stopped.

In the A1281134 trial, a total of 193 subjects were treated with ziprasidone and 90 subjects were treated with placebo in a 2:1 randomization. Subject overall mean age was 15.3 years in the ziprasidone group and 15.4 years in the placebo group, and most had a primary diagnosis of schizophrenia, paranoid type. While more subjects in the ziprasidone group completed the study (69.9% vs 57.8% in the placebo group), more subjects in the placebo group discontinued due to insufficient clinical response (20.0% vs 9.3% in the ziprasidone

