group). In this study, oral ziprasidone failed to demonstrate superiority in efficacy over placebo in adolescent subjects. Overall, ziprasidone was safe and generally well-tolerated. The higher incidence of AEs in the ziprasidone group was primarily attributed to known, pharmacologic nervous system effects (ie, somnolence, extrapyramidal disorder, tremor, akathisia, insomnia, headache, fatigue, dizziness, nausea, vomiting). The most commonly occurring AEs (all causality) in the ziprasidone group were somnolence (19.2%) and extrapyramidal disorders (11.4%). While the incidence of treatment-emergent AEs (all causality) related to extrapyramidal symptoms was higher in the ziprasidone group (24.9% in ziprasidone group vs 5.6% in the placebo group), evaluation of these symptoms using the Movement Disorder Scales did not reveal statistically significant differences between the treatment groups. The incidence of SAEs in the ziprasidone group compared to placebo was 4.7% vs 1.1%, respectively; none of the SAEs were considered treatment related. The SAEs in the ziprasidone group were suicidal ideation, anxiety, depression, psychotic disorder, schizophrenia, auditory hallucination, hostility, impulsive behavior and overdose. The SAEs in the placebo group were aggression and psychotic disorder. Suicidality was assessed using the Columbia Classification system for Possibly Suicide Related Adverse Events (PSRAEs). Four PSRAEs in the ziprasidone group were considered SAEs (suicidal ideation and self-injurious behavior, intent unknown, in 2 subjects each). Changes in BP and pulse rate were not clinically significant. Two subjects had a QTcF increase of ≥ 460 msec but < 500 msec. Two subjects treated with ziprasidone had AEs of QTcF prolonged (1 mild and 1 moderate) leading to discontinuations from the study. Ziprasidone did not have clinically significant effects on weight and metabolic indices such as fasting glucose and lipids.

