5.5. Concomitant Medication(s)

The start and stop date, if applicable, for all concomitant medications received for the disease under study within 1 year before screening and for all other concomitant medications within 90 days before screening until the last scheduled visit will be recorded on the appropriate CRF.

Subject must be willing and able to discontinue any medications that are prohibited in this study (see [table below](#)). Any such medications must be discontinued according to the timelines in the [table](#) prior to the administration of study medication. Exclusionary medications may have to be tapered instead of being abruptly discontinued if appropriate, in accordance with accepted medical practice.

Lorazepam (oral or intramuscular) may be used pro re nata (PRN) for anxiety or agitation up to a maximum of 2 mg/day but should not be given within 6 hours prior to an efficacy assessment. If possible, the investigator should start with a low dose of lorazepam to control a subject's symptoms, and then increase incrementally up to a total of 2 mg/day, if needed. A comparable benzodiazepine may be used in place of lorazepam with prior permission from Pfizer. The dose administered should be therapeutically comparable to that for lorazepam.

For the treatment of insomnia, lorazepam may be used as specified above, or alternatively, diphenhydramine or zolpidem, as determined by the principal investigator, are permitted on a PRN basis, but should not be given within 6 hours prior to efficacy assessments being performed.

For the treatment of extrapyramidal symptoms that may appear during the trial, benztropine, benhexol, other anticholinergics, or propranolol may be used based on the discretion of the principal investigator.

Subjects should be instructed not to take any medications, including over-the-counter products, without first consulting the investigator, unless such medications are for emergency use.

The chronic use of certain medications (some hormones, antihypertensives, diuretics, and oral hypoglycemics) are allowed if the subject was prescribed these medications at least 30 days prior to screening, the subject's condition is stable, and the dose is stabilized prior to the first dose of study medication.

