7.2.8. Movement Disorder Scales

The following scales will be used to assess symptoms and findings related to Parkinsonism, akathisia, and abnormal involuntary movements. Investigators will be instructed to record movement disorders as adverse events (AEs) only if they are clinically meaningful. Specifically, investigators will be asked to record the disorder as an adverse event only if (1) clinically meaningful movement disorder side effects are observed or are volunteered by the subject, (2) a clinically meaningful movement disorder is present at baseline and increases in severity, or (3) concomitant therapy (benztropine, benzhexol, or other anticholinergics or propranolol) is initiated or reinstated for movement disorders while the subject is participating in the study. All dystonic movements are to be recorded as AEs unless present at the same severity at baseline.

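### Movement-disorder scales are compared between arms only as by-visit mean change, which may be insensitive to transient or treated extrapyramidal symptoms; one subject-level table would close most of the gap

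*SAP*

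**What the plan says.** SAP 8.2.6 and Protocol 9.9 treat the three movement scales alike. Every measure in this group is first summarised in the same way: "descriptive statistics (n, mean, standard deviation, min, max, 95% CI) by treatment group and visit for the change from baseline will be provided". The movement scales then get one inferential analysis: "In addition, the same change from baseline MMRM model used for the primary and secondary endpoints will be applied to the Movement Disorder Scales". Neither section names the visit, or average of visits, on which the comparison is to be read. Neither defines a worst value, a worsening category, or a rule for scores taken after anti-EPS treatment starts.

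Other safety measures in the same SAP do get subject-level summaries: categorical QTc increases (8.2.5), and an any-visit listing for high CDRS-R totals and new-onset or worsening tables for C-SSRS (both 8.2.6).

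Two protocol sections affect what the scales and the AE data will show. Under Protocol 5.5, "For the treatment of extrapyramidal symptoms that may appear during the trial, benztropine, benhexol, other anticholinergics, or propranolol may be used". Protocol 7.2.8 says: "Investigators will be instructed to record movement disorders as adverse events (AEs) only if they are clinically meaningful". It then lists the qualifying situations, which include any start or restart of anticholinergic or propranolol treatment for a movement disorder, and it requires dystonic movements to be recorded unless unchanged from baseline.

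**The concern.** EPS usually affects a minority of subjects, and not all at the same visit. If it appears once and is treated, the later scores fall back, so a mean at any one visit carries only a fraction of the affected subjects.

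The sponsor's earlier adolescent schizophrenia trial (A1281134, Protocol 1.2.2.1.3) shows that the two kinds of measure can disagree. EPS adverse events were "24.9% in ziprasidone group vs 5.6% in the placebo group", yet "evaluation of these symptoms using the Movement Disorder Scales did not reveal statistically significant differences between the treatment groups". The protocol does not state how those scales were analysed.

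Safety and tolerability is a primary objective here. A non-significant MMRM on SARS, BAS and AIMS could be read as reassurance about EPS in children when it partly reflects dilution.

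**Working it through.** **Sample size.** The plan gives no power figure for the movement scales. The SAP's own size is reproduced first: 111/0.80 = 138.75 (SAP 2.2.1 states approximately 138), plus 18 gives 156, or 78 per arm. The protocol still states 194 (97 per arm); the direction of the result is the same.

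**The earlier trial.** In that trial, "a total of 193 subjects were treated with ziprasidone and 90 subjects were treated with placebo in a 2:1 randomization". Then 0.249 × 193 ≈ 48 and 0.056 × 90 ≈ 5. The risk difference is 48/193 − 5/90 = 19.3 points (95% CI 11.6 to 27.0), Fisher p = 0.00006. The AE contrast was strong.

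**Assumptions for the scales.** The documents give no SD, rise size or cut-off, so these are assumed: 24.9% v 5.6% affected; a rise of 3 or 5 points at one of four visits chosen at random; Poisson background with mean 0.5 (variance 0.5); no dropout.

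**Week 4 contrast, rise 3, independent visits.**
- Expected difference: 0.193 × 3/4 = 0.145.
- Proportions raised at Week 4: 0.249/4 = 0.0623 and 0.056/4 = 0.014.
- Variances: 0.5 + 9 × 0.0623 × 0.9377 = 1.025, and 0.5 + 9 × 0.014 × 0.986 = 0.624.
- SE = √[(1.025 + 0.624)/78] = 0.145, so z = 1.00 and power = Φ(1.00 − 1.96) ≈ 17%.
- With rise 5: difference 0.241, SE 0.190, power about 24-25%.

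**Visit-averaged contrast, rise 3.** The expected difference is the same, but the noise is smaller.
- Variances: 0.125 + 0.75² × 0.249 × 0.751 = 0.230, and 0.125 + 0.75² × 0.056 × 0.944 = 0.155.
- SE = √(0.385/78) = 0.070, so z = 2.06 and power ≈ 54%.
- With rise 5: difference 0.241, SE 0.0895, z = 2.70, power ≈ 77%.

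**Simulation over rises of 3 to 5 and within-subject correlation 0 to 0.5.**

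| Comparison, EPS at one visit | Power |
|---|---|
| Week 4 mean change | 17-24% |
| Mean change averaged over visits | 45-77% |
| Subjects with worst rise of 3 or more | 62-90% |

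If EPS persists once it appears, the Week 4 mean change has 80-90% power. A second model, with shifts of 2 to 3 within-visit SDs and a 2-SD cut, points the same way. For one-visit EPS it gives 9-12% at Week 4 against 34-67% for the worst value; for EPS at all visits, 53-71% against 63-79%.

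**Early leavers.** Protocol 6.4 and 6.7 require the Week 4 assessments at early termination, but SAP Appendix 2 re-slots only YMRS, CGI-S and CGI-I. With rises of 3 and 5, if the exit score stays at the nominal last visit, Week 4 power is 83% and 91%. If affected subjects' scores are lost, it is about 20-31%. The SAP does not say which applies.

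**The AE route.** A pooled count at 24.9% v 5.6% has 91% power at 78 per arm (exact Fisher). The commonest single EPS term in the earlier trial was 11.4% on ziprasidone. If its placebo rate is assumed to be 1-3%, power for that term alone is about 38-70% (an exact Fisher calculation gives 41-72%). The chance that a term reaches the tier-2 threshold of 4 cases among 78 is 21% at a true rate of 3%, 55% at 5% and 98% at 11.4%. Below the threshold a tier-3 term gets a simple proportion and no interval.

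**The case against.** The strongest reply is that EPS already has its own route. Protocol 7.2.8 makes every start of anti-EPS treatment and every new or worsened dystonia an AE, so treated EPS should not go unrecorded. AEs in tiers 1 and 2 are compared by risk difference with 95% CI (SAP 8.2.5), and AE incidence is what showed the excess in the earlier trial. Concomitant medications are tabulated by arm. The by-visit minimum and maximum are reported for the scales. The sample code in SAP Appendix 1.1 requests treatment differences at each visit and averaged over visits, so a Week 4-only power figure understates what the MMRM will show.

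Most of that stands, and it rules out three stronger readings that a reader might draw:
- **That the earlier trial failed with this same method.** Protocol 1.2.2.1.3 does not give its scale method.
- **That EPS will be missed.** The AE rules contradict this for treated EPS and dystonia.
- **That the loss is the full distance between the Week 4 figure and the worst-value count.** Week 4 is the primary time point for YMRS; no such choice is stated for these scales.

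The reply does not supply a count of worsened subjects on any movement scale, a dedicated count of new anti-EPS drug starts, or a pooled EPS group in the SAP text. The tier-1 list may contain such a group, but that cannot be checked from these documents. Untreated, non-dystonic cases still depend on the investigator judging them clinically meaningful.

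**Conclusion.** The point holds as a limited gap. The only between-arm comparison of the movement scales is by-visit mean change, and this may be insensitive to transient or treated EPS. Against the visit-averaged contrast, the fairer comparator, a worst-value count raises power from about 45-77% to 62-90% when EPS appears at one visit. There is little or no gain when EPS persists. On the AE side, pooling gives 91% against about 38-70% for the commonest single term.

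These figures rest on assumed rise sizes, background scores, correlation and cut, and on the earlier trial's EPS rates carrying over from adolescents with schizophrenia to this population. The direction was the same in both models for one-visit EPS; the exact sizes should not be relied on. The primary efficacy analysis is unaffected. This is a cheap improvement to the reporting of a primary safety objective, not an error that invalidates the plan.

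**What to change.** Keep the MMRM. In SAP 8.2.6, add one pre-specified table giving, per arm, the number and percentage of subjects with the risk difference and 95% CI, for:

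- (a) any AE in a pre-listed, pooled EPS term group (if the Safety Review Plan already holds such a group, cite it);
- (b) a new anti-EPS drug started after the first dose;
- (c) a worst post-baseline rise above a stated cut on each of SARS, BAS global and AIMS 1-7, counting the early-termination visit.

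Report each component separately. Fix the term list, drug list and cuts before unblinding. The 3-point rise used above illustrates the method and is not a recommended cut. State also which MMRM contrast is to be read for these scales and how early-termination scores enter it.

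The cost is one exploratory table from data already collected, some SAP wording and a choice of cut points. No new assessment or change in conduct is needed.
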